5.2.7	Prior Medications and Concomitant Medications/Procedures.....	12
5.2.8	Study Drug Exposure and Compliance	12
5.3	Efficacy Endpoints and Analyses.....	13
5.3.1	Co-Primary Endpoint Analysis	13
5.3.2	Secondary and Exploratory Efficacy Endpoint Analyses	14
5.3.3	Sensitivity Analyses for Efficacy Endpoints	15
5.3.4	Exploratory Endpoints	16
5.4	Safety Endpoints and Analyses	17
5.4.1	Adverse Events (AEs).....	17
5.4.2	Adverse Events of Special Interest (AESIs)	18
5.4.3	Laboratory Evaluations	19
5.4.4	Physical Examinations (PEs)	21
5.4.5	Vital Signs.....	22
5.4.6	Electrocardiogram (ECG)	22
6	Reference	22
7	Appendices.....	23

1 List of Abbreviations

Abbreviation or Specialist Term	Explanation
AE	Adverse event
AESI	Adverse events of special interest
ALB	Albumin
ALK-P	Alkaline phosphatase
ALT	Alanine aminotransferase
ANCOVA	Analysis of covariance
ApoB	Apolipoprotein B
ASCVD	Atherosclerotic cardiovascular diseases
AST	Aspartate aminotransferase
ATC	Anatomical therapeutic classification
BA	Bempedoic acid
BMI	Body mass index
BP	Blood pressure
BUN	Blood urea nitrogen
Ca	Calcium
CI	Confidence interval
CK	Creatine kinase
CO ₂	Carbon dioxide
CRF	Case Report Form
CRO	Contract research organization
CV	Cardiovascular
DBP	Diastolic blood pressure
eCRF	Electronic case report form
ECG	Electrocardiogram
eGFR	Estimated glomerular filtration rate
EOS	End of Study
EZE	Ezetimibe
FAS	Full analysis set
FDA	Food and drug administration
FDC	Fixed-dose combination
FSH	Follicle-stimulating hormone
Hct	Hematocrit
HDL-C	High-density lipoprotein cholesterol
HeFH	Heterozygous familial hypercholesterolemia
hs-CRP	High-sensitivity C-reactive protein
ICH	International Conference on Harmonisation
IMP	Investigational medicinal product
IND	Investigational New Drug Application
INR	International normalized ratio
IWRS	Interactive web response system
LDH	Lactate dehydrogenase

Abbreviation or Specialist Term	Explanation
LDL-C	Low-density lipoprotein cholesterol
LSM	Least square mean
MCH	Mean corpuscular hemoglobin
MCHC	Mean corpuscular hemoglobin concentration
MCV	Mean corpuscular volume
MedDRA	Medical Dictionary for Regulatory Activities
non-HDL-C	Non-high-density lipoprotein cholesterol
PE	Physical examination
PK	Pharmacokinetic(s)
PMM	Pattern mixture model
PT	Preferred term
RBC	Red blood cell
SAS	Statistical analysis system
SAE	Serious adverse event
SAP	Statistical Analysis Plan
SBP	Systolic blood pressure
SD	Standard Deviation
SE	Standard error
SGOT	Serum glutamic oxaloacetic transaminase
SGPT	Serum glutamic pyruvic transaminase
SOC	System organ class
SP	Safety population
TB	Total bilirubin
TC	Total cholesterol
TEAE	Treatment-emergent adverse event
TG	Triglycerides
TSH	Thyroid-stimulating hormone
ULN	Upper limit of normal
WBC	White blood cell
WHO	World Health Organization

2 Introduction

The purpose of this document is to describe the statistical methods, data derivations and data summaries to be employed in ETC-1002FDC-053. The preparation of this statistical analysis plan (SAP) has been based on International Conference on Harmonisation (ICH) E3 and E9 Guidelines and in reference to Protocol ETC-1002FDC-053 (Protocol Amendment 1, October 18, 2017).

The SAP will supersede the protocol in the event of any differences between the two documents in the plans for data analysis, and the protocol will be amended if appropriate. The SAP will be included as an appendix in the clinical study report for this protocol.

3 Study Objectives and Endpoints

3.1 Objectives

The co-primary objectives are to assess LDL-C lowering efficacy in patients receiving maximally tolerated statin therapy and treated for 12 weeks with BA 180 mg + EZE 10 mg FDC versus each of the following:

- Placebo
- BA 180 mg
- EZE 10 mg

The secondary objectives are:

- To assess the efficacy of BA 180 mg + EZE 10 mg FDC versus placebo alone, BA alone, and EZE alone on high-sensitivity C-reactive protein (hs-CRP), non-HDL-C, TC, ApoB, HDL-C, and TG after 12 weeks of treatment
- To characterize the safety and tolerability of BA 180 mg + EZE 10 mg FDC versus BA alone, EZE alone and placebo alone through 12 weeks of treatment

The exploratory objectives are:

- To assess the efficacy BA 180 mg + EZE 10 mg FDC versus placebo alone, BA alone, and EZE alone on percentage of patients attaining LDL-C <70 mg/dL after 12 weeks of treatment
- To characterize the plasma trough concentrations of BA and/or EZE when administered as BA 180 mg + EZE 10 mg FDC, BA alone, and EZE alone

3.2 Endpoints

The following endpoints will be used to evaluate the objectives of the study.

3.2.1 Primary Endpoint

- Percent change from baseline to Week 12 in LDL-C

3.2.2 Secondary Endpoint

- Percent change from baseline to Week 12 in hs-CRP, non-HDLC, TC, ApoB, HDL-C, and TG.

3.2.3 Exploratory Endpoints

- Percentage of patients attaining LDL-C <70 mg/dL after 12 weeks of treatment.
- Plasma trough concentrations at Weeks 4, 8, and 12 of BA (ETC 1002 and its active metabolite ESP15228) and EZE (glucuronidated EZE and unconjugated EZE) in BA 180 mg + EZE 10 mg FDC-treated arm, BA-treated arm, and/or EZE alone treated arm.

3.2.4 Safety Endpoints

- Patient incidence of adverse events (AEs)
- Clinical safety laboratory (including hematology, blood chemistry, and urinalysis) results
- Vital signs, electrocardiograms (ECGs) and physical examination (PE) findings

4 Study Design

4.1 Study Design

This is a Phase 3, randomized, double-blind, parallel group, multicenter study of BA + EZE versus its individual components and placebo. Screening (S1) will occur approximately within 2 weeks prior to randomization. Patients who are deemed not eligible for randomization at any point during screening will be notified by clinical site personnel regarding their eligibility status and considered screen failures. Approximately 350 eligible patients will be randomized 2:2:2:1 on Day 1/Week 0 (T1) to receive either BA 180 mg + EZE 10 mg FDC (N = 100), BA 180 mg (n = 100), EZE 10 mg (n = 100), or placebo (n = 50) for 12 weeks. Randomized patients will return for clinic visits at Week 4 (T2), Week 8 (T3) and Week 12 (T4). Patients who withdraw from investigational medicinal product (IMP) treatment will be asked to continue to be followed for safety and efficacy using the protocol-specified visit schedule and procedures.

[figure not shown]
Eligible patients will have documented atherosclerotic cardiovascular diseases (ASCVD), heterozygous familial hypercholesterolemia (HeFH), and/or multiple cardiovascular risk factors and require additional LDL-C-lowering therapy despite receiving maximally tolerated statin background therapy. Maximally tolerated statin therapy may include

statin regimens other than daily dosing or no statin at all (if not tolerated); however, doses of simvastatin ≥ 40 mg/day are prohibited. A patient's currently used and maximally tolerated statin therapy will be determined by the investigator based on their medical judgment and local standard of care. Available sources, including the patient's self-reported history of lipid-modifying therapy will also be considered.

Patients will be stratified based on baseline/current statin intensity (high intensity statin versus other) and disease characteristics (ASCVD and/or HeFH versus multiple CV risk factors). High intensity statin includes atorvastatin 40-80 mg/day and rosuvastatin 20-40 mg/day, all others will be categorized as 'other' for randomization and stratification purposes. Definition of ASCVD and/or HeFH or multiple CV risk factors are provided in inclusion criteria. Enrollment will be monitored and a cap may be placed, if necessary, to ensure appropriate distribution into either of the statin intensity categories.

The Study Flow Chart is presented in Figure 1.

Figure 1: Study Flow Chart

For details of study assessments, see the Schedule of Events in [Appendix 1](#).

4.2 Randomization

[figure not shown]
During the Treatment Period, patients will receive double-blind IMP. At Day 1 (Visit T1), patients will be randomized to receive either BA 180 mg + EZE 10 mg FDC, BA 180 mg, EZE 10 mg or placebo with 2:2:2:1 ratio.

The randomization will be stratified by baseline statin intensity (high intensity vs. other) and disease characteristics (ASCVD and/or HeFH vs. multiple CV risk factors). Only atorvastatin 40-80 mg/day and rosuvastatin 20-40 mg/day are considered high intensity statin and all others will be considered as 'other' for randomization purpose.

The criteria for determining these 2 stratification factors are further detailed in criteria for selection of patients in protocol. The investigator or designee will utilize IWRS during the visit to randomize the patient and obtain the appropriate IMP container via medication identification numbers. A patient is considered to be randomized when the corresponding randomization box is checked within the eCRF.

4.3 Sample Size Justification

The sample size of 100 patients per active treatment group and 50 patients in the placebo arm (2:2:2:1) of this study (350 patients total) was selected to provide adequate power for each of the co-primary endpoint as well as the co-primary endpoint family as a whole.

5 Statistical and Analytical Plans

5.1 General Statistical Considerations

In general, summary statistics for continuous variables will include the number of patients, mean, median, SD or standard error (SE), first and third quartiles, minimum, and maximum. Minimum and maximum will be presented same number of decimal places as reported/collected, one additional decimal place for mean and median, and two additional decimal places for SD.

For categorical variables, the frequency and percentage will be given. Percentage will be presented with one decimal place. All categories will be presented (even if no patients are counted in the category). Counts of zero in any category will be presented without percentage.

Data will be presented on listings in order of patient, assessment date and assessment (in order collected on CRF, unless specified otherwise). Dates will be presented in format DDMMYY YYYY.

The visit schedules and window are shown below.

Visit	S1	T1	T2	T3	T4
Slotted Study Week	-2	0	4	8	12/EOS
Target Study Day	Day -13	Day 1	Day 29	Day 57	Day 85
Analysis Visit Windows	$[-\infty, -1]$	[1]	[2,34]	[35, 62]	$[63, +\infty]$
Protocol defined visit window	Day -16 to -5	Day 1	Day 29 ± 5	Day 57 ± 5	Day 85 ± 5

5.2 Statistical Analysis Plans

5.2.1 Analysis Population

5.2.1.1 Full Analysis Set (FAS)

The full analysis set (FAS), used for all of the efficacy analyses, is defined as all randomized patients. Patients in FAS will be analyzed in the treatment group they are randomized to regardless of the treatment received.

5.2.1.2 Safety Population (SP)

The Safety Population (SP), used for all of the safety summaries, is defined as all randomized patients who received at least 1 dose of blinded IMP. Patients in the SP will be included in the treatment group that they actually received, regardless of their randomized treatment.

5.2.1.3 Treatment Completer Analysis Set

Treatment completer analysis set a subset of full analysis set and will include subjects who complete 12-week treatment as indicated on the end of treatment CRF and have non-missing LDL-C value at Week 12.

5.2.1.4 PK Analysis Set (PKS)

The PK analysis set (PKS), used for all of the PK-related summaries, is defined as all patients in the SP who have at least 1 PK assessment unless major protocol deviations are identified to have affected the PK data or if key dosing or sampling information is missing. All PK samples with data available will be included in the summary unless the sample time is outside of 18 to 30 hours window since last dose of study drug or dosing and/or sampling time are missing. PK result listing will list all results regardless of sampling window.

5.2.2 Baseline Definition

Baseline LDL-C is defined as the mean of the values from Week -2 (Visit S1) and pre-dose Day 1/Week 0 (Visit T1) (i.e., the last two non-missing values on or prior to Day 1). If only one value is available then that single value will be used as baseline.

Baseline for non-HDL-C, HDL-C, TC, and TG is defined as the mean of the values

from Week -2 (Visit S1) and pre-dose Day 1/Week 0 (Visit T1) (i.e., the last two non-missing values on or prior to Day 1). If only one value is available then that single value will be used as baseline.

Baseline for ApoB and hs-CRP is defined as the pre-dose Day 1/Week 0 (Visit T1) value (i.e. the last non-missing value on or prior to Day 1). If this is not available, then the last non-missing value prior to the first dose of double-blind study medication (including unscheduled assessments) will be used as baseline.

Baseline of other laboratory parameters, vital signs and physical examination is defined as the last non-missing value prior to the first dose of study drug.

5.2.3 Protocol Violations and Deviations

A full list of protocol violations and deviations will be compiled and reviewed by the clinical team to identify major versus minor violations/deviations before final database lock. For violations at study entry, patients will be assessed against the inclusion and exclusion criteria of the protocol. For on-study deviations, compliance with the protocol will be examined using blinded review of the source data with regard to prohibited therapies, and timing and availability of planned assessments. The determination of major versus minor protocol deviations will be conducted prior to the database lock. Any protocol deviation related to inclusion/exclusion criteria will be summarized in table as well as listing. Any major on-study protocol deviation will also be summarized by treatment group, and all protocol deviations will be listed.

5.2.4 Patient Disposition

Disposition, including reason for withdrawal from IMP and the study, will be summarized by treatment group. In addition, the number of patients who withdraw from the study and withdraw from study drug will be summarized by discontinuation reason.

5.2.5 Demographic and Baseline Characteristics

Demographic information and patient baseline characteristics including, but not limited to, gender, race, age, and baseline vital signs will be summarized by treatment group.

The following demographic and baseline characteristics will be summarized by treatment group, as well as overall, for safety population and for FAS population: age (years), age will be summarized as a continues variable and by age group (18-40, 41-64, 65-74, and ≥ 75), gender, race, ethnicity, height (cm), weight (kg), body mass index (BMI) (kg/m^2), BMI group (<25 , $25-30$, ≥ 30 kg/m^2), eGFR, systolic and diastolic blood pressure (mmHg), heart rate, history of diabetics and hypertension, background statin therapy, disease characteristics, tobacco history, alcohol history, fasting lipid parameters (TC [mg/dL], calculated LDL-C [mg/dL], HDL-C [mg/dL], non-HDL-C [mg/dL] and TG [mg/dL]), ApoB(mg/dL), and hs-CRP (mg/dL).

Data will be summarized using descriptive statistics for continuous variables and using counts and percentages for categorical variables by treatment group and overall.

5.2.6 Subgroups Variables

- 1) Gender (male vs. female)
- 2) Age (< 65 yrs. vs. \geq 65 yrs.)
- 3) Baseline CVD risk category (ASCVD and/or HeFH vs. multiple CV risk factors)
- 4) Baseline statin intensity (high intensity vs. other)
- 5) Race (white vs. other)
- 6) Baseline LDL category (< 130 mg/dL vs. \geq 130 - <160 mg/dL vs. \geq 160 mg/dL) (efficacy only)
- 7) History of diabetes (yes vs. no)
- 8) Body Mass Index (BMI) (< 25, 25 - < 30, \geq 30 kg/m²)

In case the number of patients within a subgroup is too small for a meaningful analysis, the analyses may not be performed or the subgroup levels may be combined.

5.2.7 Medical History

General medical history will be summarized by treatment group by system organ class (SOC) and preferred term (PT) using Medical Dictionary for Regulatory Activities (MedDRA), as well as overall, for safety population and presented in a by-patient listing. Where appropriate, terms will be coded using the latest version of MedDRA.

5.2.8 Prior Medications and Concomitant Medications/Procedures

Prior medications are defined as medications that ended prior to the initiation of double-blind study drug. Concomitant medications are defined as medications that were ongoing at the time of double-blind study drug initiation or new medications that started post double-blind study drug initiation and within 30 days following the date of the last dose of study drug.

Medications, including prior statin medications, will be coded using WHO Drug (Sept 2016, or later). The frequency of use of prior medications and use of concomitant medications will be summarized by treatment group, as well as overall, for the safety population according to Anatomical Therapeutic Chemical (ATC) class and preferred term. Prior medications, concomitant medications, and concomitant procedures will be listed for each patient.

5.2.9 Study Drug Exposure and Compliance

The length of exposure to study drug (FDC, BA, EZE or placebo) will be calculated as the number of days from the first dose of double-blind study drug to the last dose of double-blind study drug, regardless if the patient missed one or more doses of study drug. Length of exposure will be summarized by treatment group using descriptive statistics for the safety population.

The overall compliance to study drug calculated based on tablet count will be summarized by treatment group using summary statistics. The number and percentage of patients who were compliant with taking study drug will be summarized by treatment group for the safety population for the following categories <80%; >= 80%. Overall compliance will be calculated as: $100 * (\text{Total Dispensed Tablets} - \text{Total Returned Tablets}) / \text{Treatment Duration in day}$. Overall compliance during the study will be calculated by using study drug dispensation data.

The study drug administration and compliance data, including reasons for poor compliance, will be listed for each patient.

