13. History within the last 2 years of drug, alcohol, amphetamine and derivatives, or cocaine abuse. Patients with amphetamine derivatives prescribed by and under the care of a health care practitioner can be enrolled after evaluation by the Investigator;
14. Blood donation, blood transfusion, participation in a clinical study with multiple blood draws, major trauma, or surgery with or without blood loss within 30 days prior to randomization;
15. Use of any experimental or investigational drugs within 30 days prior to screening;
16. Previous enrollment in a BA clinical study;

17. Use of any of the following drugs within 5 weeks prior to screening (Visit S1) unless otherwise stated or a plan to use these drugs during the study is **prohibited**:

- Systemic corticosteroids. Topical and inhaled corticosteroids are allowed;
- Simvastatin ≥ 40 mg/day;
- Non-statin LDL-C-modifying therapies:
 - Fibrates (including fenofibrate);
 - Niacin and derivatives;
 - Bile acid sequestrants;
 - Ezetimibe;
 - Mipomersen or lomitapide (6 months prior to screening);
 - Apheresis;
 - Proprotein convertase subtilisin/kexin type 9 (PCSK9) inhibitors (4 months prior to screening except PCSK9 small interfering RNA (siRNA), which are prohibited if used at any time in the past);
 - Cholesteryl ester transfer protein (CETP) inhibitors (12 months prior to screening);
 - Red yeast rice extract-containing products (2 weeks prior to screening);

18. Starting or adjusting the dose of the following permitted drugs within 5 weeks prior to screening. These drugs are **allowed as long as stable** at least 5 weeks prior to screening (Visit S1) unless otherwise noted:

- Hormone replacement;
- Thyroid replacement;
- Obesity medication (6 months prior to screening);
- Omega 3 fatty acids;
- Diabetes medications;

19. Previous intolerance to ezetimibe;

20. A medical or situational (ie, geographical) finding that in the investigator's opinion may compromise the patient's safety or ability to complete the study;

21. An employee or contractor of the facility conducting the study, or a family member of the Principal Investigator, Co-Investigator, or Sponsor.

Investigational Medicinal Product, Dosage and Mode of Administration:

- BA 180 mg + EZE 10-mg FDC tablet and matching placebo tablet
- BA 180-mg tablet and matching placebo tablet
- EZE 10-mg capsule and matching placebo capsule

All IMP will be ingested once daily at a similar time with or without food.

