8. TREATMENT OF PATIENTS

8.1. Administration of Investigational Medicinal Product

During the Treatment Period, patients will be randomized to receive IMP of either BA 180 mg + EZE 10 mg FDC, BA 180 mg, EZE 10 mg, or placebo once daily. Each daily allotment of IMP is comprised of 2 tablets and 1 capsule provided in a blister package. Patients will be instructed to ingest IMP orally once daily with or without food at a similar time every day. On clinic visit days, patients will be instructed to delay ingestion of IMP until all study procedures have been completed.

If the patient forgets to take IMP on nonclinic visit days, it may be taken up to 12 hours later the same day. After that time, the patient should not take IMP that day and should resume ingestion of IMP the following day. Details describing the reasons for missed doses should be documented in the patient's medical records and electronic case report form (eCRF). Extra IMP is provided and can be used, if needed, prior to the next visit or to replace an allotment of IMP that cannot be used because it is lost or damaged.

Other details regarding IMP, including description, supply and control, accountability, handling, and disposal are provided in [Section 9](#).

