9. INVESTIGATIONAL MEDICINAL PRODUCT

9.1. Description of Investigational Medicinal Product

Table 2: Investigational Medicinal Products

Product Name:	Investigational Medicinal Product	
	Bempedoic acid	Placebo to Match Bempedoic Acid
Dosage Form:	Film-coated tablets	Film-coated tablets
Unit Dose:	180 mg	Not applicable
Container/Closure:	9 count blister card with child resistant closures	9 count blister card with child resistant closures
Route of Administration:	Oral, daily at approximately the same time, with or without food	Oral, daily at approximately the same time, with or without food
Physical Description:		
Product Name:	Investigational Medicinal Product	
	Ezetimibe	Placebo to Match Ezetimibe
Dosage Form:	Over-encapsulated tablets	Capsules
Unit Dose:	10 mg	Not applicable
Container/Closure:	9-count blister card with child-resistant closures	9-count blister card with child-resistant closures
Route of Administration:	Oral, daily at approximately the same time, with or without food	Oral, daily at approximately the same time, with or without food
Physical Description:		
Product Name:	Investigational Medicinal Product	
	Bempedoic acid + ezetimibe FDC	Placebo to Match Bempedoic acid + ezetimibe FDC
Dosage Form:	Tablets	Tablets
Unit Dose:	180 mg/10 mg	Not applicable
Container/Closure:	9-count blister card with child-resistant closures	9-count blister card with child-resistant closures
Route of Administration:	Oral, daily at approximately the same time, with or without food	Oral, daily at approximately the same time, with or without food
Physical Description:		

Please see Pharmacy Manual for detailed storage requirements and instructions and additional information.

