9.4. Investigational Medicinal Product Adherence

At each clinic visit during the Treatment Period, designated clinical site staff will assess patient IMP intake adherence by counting the number of tablets that are returned as unused and by querying the patient with regards to daily intake. If the patient has not taken multiple doses as instructed, the patient will be queried for a reason, findings will be documented, and the patient will be counseled on the importance of carefully following all dosing instructions. Factors contributing to poor adherence will be determined and, if possible, remedied. Patients demonstrating poor adherence during the Treatment Period will continue to be counseled on the importance of carefully following all dosing instructions, but will not be removed from the study.

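### The planned compliance table counts tablets only, so in the ezetimibe arm it scores placebo tablets and does not respond to intake of the active capsule

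*SAP*

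**What the plan says.** SAP 5.2.9 sets the basis of the summary: "The overall compliance to study drug calculated based on tablet count will be summarized by treatment group using summary statistics". The formula there is 100 times (tablets dispensed minus tablets returned), divided by treatment duration in days. Patients are then grouped "for the following categories <80%; >= 80"%. Capsules are not mentioned.

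At the sites, Protocol 9.4 has staff assess adherence by "counting the number of tablets that are returned as unused and by querying the patient with regards to daily intake".

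On what is taken, Protocol 8.1 says: "Each daily allotment of IMP is comprised of 2 tablets and 1 capsule provided in a blister package". The Synopsis lists the FDC and BA products as tablets with matching placebo tablets, and the single-agent ezetimibe product as "EZE 10-mg capsule and matching placebo capsule". Protocol Table 2 (section 9.1) gives its dosage form as "Over-encapsulated tablets".

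**The concern.** The design is double-dummy, so each arm carries its active drug in a different unit. In the EZE arm both tablets are placebo and the capsule is the only active unit. A tablet count therefore includes the active unit in the FDC and BA arms (one active and one placebo tablet a day) and omits it in the EZE arm. One table, laid out by arm under one label, then measures different things in different columns.

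This matters for interpretation because FDC versus EZE is one of three co-primary comparisons, all of which must succeed. A reader who wants to know whether the active comparator was taken will look at this table first. For that arm, it reports placebo intake.

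**Working it through.** The documents state no expected compliance figure, so there is nothing to reproduce. The check is to apply the SAP 5.2.9 rule to defined intake patterns.

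**Inputs**
- Daily allotment in every arm: 2 tablets and 1 capsule (Protocol 8.1).
- Duration: 12 weeks, taken as 12 × 7 = 84 days.
- Full intake: 2 × 84 = 168 tablets and 84 capsules, 252 units in all.
- Cut-off: 80% (SAP 5.2.9).

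**Formulas**
- A, SAP as written: 100 × tablets taken / 84.
- B, tablets with the divisor corrected: 100 × tablets taken / 168.
- C, all units pooled with a corrected divisor: 100 × (tablets + capsules) / 252.
- D, capsules alone: 100 × capsules taken / 84.

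**Results**

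| Intake pattern | A | B | C | D (active unit in EZE arm) |
|---|---|---|---|---|
| Everything | 200% | 100% | 100% | 100% |
| All tablets, no capsules | 200% | 100% | 66.7% | 0% |
| No tablets, all capsules | 0% | 0% | 33.3% | 100% |
| All tablets, 40% of capsules | 200% | 100% | 80.0% | 40% |
| 40% of everything | 80.0% | 40% | 40% | 40% |

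Arithmetic for the less obvious cells:
- Row 1, A: 100 × 168 / 84 = 200%.
- Row 2, C: 100 × 168 / 252 = 66.7%.
- Row 4, C: 100 × (168 + 33.6) / 252 = 80.0%.
- Row 5, A: 100 × 67.2 / 84 = 80.0%.

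**What this shows**
1. Under A, rows 1 and 2 are identical. In the EZE arm the score is the same whether the patient took all of the active drug or none. Row 3 is the reverse: all active doses taken, yet a score of 0%, in the below-80% category.
2. Correcting the divisor alone (B) leaves rows 1 and 2 identical. The capsule omission is separate from the divisor fault.
3. The divisor fault is real as well. Full tablet intake reads 200%, and a patient who takes 40% of everything falls in the 80%-or-more category. This applies in all arms.
4. Pooling all three units (C) does not isolate the active unit: a patient with 40% capsule intake still reaches 80%. Pooling without correcting the divisor gives 100 × 252 / 84 = 300% at full intake.

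**The case against.** **The word tablet may be loose.** Table 2 describes the ezetimibe unit as "Over-encapsulated tablets", and the missing factor of two could mean that the authors were thinking of a daily dose. This is possible. But the Synopsis, Protocol 8.1 and Table 2 all separate tablets from capsules when describing the supply, and the loose reading does not rescue the table: column C shows that a pooled count still hides low capsule intake.

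**Other evidence of intake exists.** This stands, and it limits the point. Protocol 9.4 adds a patient query to the count, Protocol 9.5 has all unused product returned for adherence assessment, and SAP 5.2.9 lists administration and compliance data for each patient. Protocol 12.1.6.3 measures ezetimibe troughs at Weeks 4, 8 and 12, and SAP 5.3.5 summarizes them by arm. Patients who never take the capsule are those whom troughs are best placed to expose. The troughs do not replace a compliance figure, though. They are descriptive, the summary is restricted to samples 18 to 30 hours after the last dose (SAP 5.2.1.4), and no rule turns them into an adherence category. FDC tablets and over-encapsulated ezetimibe are also different dosage forms, so a difference in mean trough between those arms is not cleanly a difference in adherence.

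**Packaging and blinding make selective omission unlikely.** The three units are supplied together in a blister package, and patients do not know which unit is active. That makes the tablet count a reasonable proxy for capsule intake, but one that cannot detect the case where the two diverge.

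**Stronger readings that the documents do not support.** A reader might infer that adherence is assessed by tablet count alone, or that the trial cannot show that ezetimibe was taken. The query, the returns and the troughs answer both. A reader might also infer that the FDC versus EZE difference is inflated. The way a table counts units changes no estimate. The documents give no rate of capsule-only omission, and the 18% LDL-C reduction cited in Protocol 4.1 is for primary hyperlipidemia, not for add-on to maximally tolerated statin. Skipped FDC tablets would act in the opposite direction. No bias figure can be supported.

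**Conclusion.** The point holds as a defect of one descriptive table. Read as written, the rule gives EZE-arm compliance, for all of the approximately 100 patients planned in that arm, as intake of placebo tablets. That figure and its 80% split are unaffected by capsule intake anywhere from 0% to 100%.

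The co-primary tests do not depend on it. The full analysis set is all randomized patients by assigned arm (SAP 5.2.1.1). The completer set uses the end-of-treatment form and a Week 12 LDL-C value (SAP 5.2.1.3). The imputation rule uses time since last dose (SAP 5.3.1). None uses the compliance percentage or the 80% category.

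The conclusion assumes that tablet means tablet, as it does in the supply descriptions. If capsules were meant to be counted too, the text needs to say so, and the pooled figure would still fail to describe the active unit. The 200% result assumes 84 days of treatment and the stated allotment of two tablets a day; the ratio is the same for any duration.

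**What to change.** **Protocol 9.4:** have sites count returned tablets and returned capsules separately at each visit. Sites remain blinded, because the same two counts are made in every arm.

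**SAP 5.2.9:** state which units are counted and compute compliance by dosage form:
- tablets: 100 × (dispensed − returned) / (2 × days);
- capsules: 100 × (dispensed − returned) / days.

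Report by arm the compliance to the unit that carries active drug (FDC tablet, BA tablet or EZE capsule), and apply the 80% split to that figure. Where the tablet types cannot be told apart on return, report tablet and capsule compliance side by side for every arm. Correct the capsule omission and the divisor together, since fixing either alone leaves the table wrong.

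**Cost:** one extra count field per visit and a small amount of programming. Unused product is already returned under Protocol 9.5, so no visit or procedure is added.
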